6.3.6 Immunologic Studies

CD4+/CD8+

Obtain absolute CD4+/CD8+ count and percentages within 60 days prior to entry and per the SOE at any US laboratory that possesses a CLIA certification or its equivalent, or at any network-approved non-US laboratory that operates in accordance with GCLP and participates in appropriate external quality assurance programs.

During the study, all laboratories must possess a CLIA certification or equivalent and must be certified for protocol testing by the DAIDS Immunology Quality Assurance (IQA) Program.

Cryopreserved PBMCs for HIV-1 Gag-specific CD8+ and CD4+ cell Immunity

PBMC for flow cytometric testing of the frequency of HIV-1 Gag-specific and other non-specific responses in CD8+ and CD4+ cells by intracellular staining for IFN-gamma will be stored for analysis. In addition, HLA genotyping will be performed (entry visit only).

Stored Plasma for Inflammatory and Coagulation Markers

Plasma for soluble markers of inflammation (including IL-6, IL-7, IL-15) will be stored for analyses.

Cryopreserved PBMCs for Markers of T-cell Activation and Proliferation

Testing for T-cell activation and proliferation (% CD4+ and CD8+ cells CD38+/HLA-DR+, CD25+, PD-1+, PD-L1, Ki67+) will be performed concomitantly to the primary immunologic objectives.

Cryopreserved PBMCs for Exploratory Studies

B cell phenotyping, rearrangements and class switching determination will also be performed on cryopreserved cells as an exploratory objective.

Stored Plasma for Antibody Quantitation

Plasma will be stored for HIV-1-specific antibody quantitation including the use of assays that measure antibody levels, avidity and the breadth of antibody responses in peptide microarrays.

6.3.7 Virologic Studies

Plasma HIV-1 RNA

Screening HIV-1 RNA must be performed within 60 days prior to study entry by the Abbott RealTime HIV-1 assay or Roche COBAS TaqMan HIV-1 Test, Version 2.0 assay at any laboratory that possesses a CLIA certification or its equivalent.

After screening, all plasma HIV-1 RNAs should be performed by the Abbott RealTime HIV-1 assay at any laboratory that possesses a CLIA certification or its equivalent. Shipping should be done in an expeditious manner, preferably the day the sample is obtained.

HIV-1 Drug Resistance Genotyping

Resistance genotyping will be performed in those individuals with confirmed HIV-1 RNA >200 copies/mL on two consecutive assessments using the sample from the first of the two time points with HIV-1 RNA >200 copies/mL. Upon confirmation of virologic failure, a sample from the first time point having a viral load at least 1000 copies/mL will be sent for HIV-1 drug resistance genotyping.

6.3.8 Viral Reservoir Studies

Cryopreserved PBMCs for Inducible RNA Assay

The quantitative **inducible RNA** assay will be performed on resting CD4+ cells obtained from cryopreserved PBMC.

Cryopreserved PBMCs for Cell-Associated RNA and DNA

The cell-associated HIV-1 RNA and DNA will be performed on cryopreserved PBMC.

NOTE: Extraction, purification and quantification of cell-associated RNA and DNA will take place simultaneously on the same cryopreserved PBMC aliquot.

Stored Plasma for Residual Viremia by Single-Copy RNA Assay

Refer to the LPC for blood volumes.

6.3.9 Gene Expression Studies

Whole blood will be stored for gene expression assays.

6.3.10 Stored Samples for Future Unspecified Assays

Plasma and PBMCs will be collected, processed, and stored for future unspecified immunologic and exploratory aims, if the allowed maximum blood volume is not exceeded.

6.3.11 Procedures

Tuberculosis Test

Purified protein derivative tuberculin skin testing (TST) will be performed at screening for **participants** with either no prior or negative TB testing. **Participants** with prior positive TB screening tests do not need to have repeat TB testing. TST sites will be evaluated for induration between 48 and 72 hours after the PPD dose is administered. An induration of ≥ 5 mm will be considered positive. TB screening may also be performed by blood tests (also called interferon-gamma release assays or IGRAs), and is the screening of choice for individuals who have received Bacillus Calmette–Guérin (BCG) vaccine. TB results do not need to be recorded on a CRF.

Chest Radiograph

At screening (after pregnancy test) a posterior-anterior (PA) and lateral chest x-ray will be performed and reviewed by site staff for evidence of lung disease including active or latent tuberculosis. Chest x-ray results do not need to be recorded on a CRF.

Anal Swabs/Anal Pap Test

Refer to the A5337 Anal Swab Instruction Sheet posted on the PSWP for processing and shipping information.

Anal swabs will be collected for HPV DNA quantification. Specimens will be frozen and stored.

Anal Pap tests will be performed at a laboratory that has CLIA certification or its equivalent and the result will be recorded on a CRF. No specimens need to be collected if anal Pap tests were done as part of routine medical care outside the study ± 4 weeks of the scheduled study visit and tested in a CLIA certified laboratory, but results need to be recorded.

Oral Swabs

Oral swabs will be collected to evaluate whether the use of sirolimus is associated with more frequent reactivation or suppression of HHV. Refer to the A5337 LPC posted on the PSWP for processing and shipping information.

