1.4 Exploratory Objectives

- 1.4.1 To assess the pharmacokinetic (PK) interactions between sirolimus therapy and antiretroviral (ARV) drug levels.
- 1.4.2 To perform ex vivo flow cytometric phenotyping of activation/proliferation in CD4+ and CD8+ central memory (CM), transitional memory (TM), effector memory (EM) and naïve populations as defined by CCR7 and CD27 expression.

- 1.4.3 To measure the effects of sirolimus on homeostatic proliferation, **gene expression and transcriptional regulation**.
- 1.4.4 To assess the impact of sirolimus on soluble markers of inflammation, including IL-6, IL-7 and IL-15.
- 1.4.5 To measure the effects of sirolimus on HIV-1-specific antibody levels, the breadth of antibody responses, and B cell phenotype, rearrangements, and class switching.
- 1.4.6 To assess the relationship between human papillomavirus (HPV) DNA levels and HPV-related disease from anal swabs and anal Pap smears prior to and at completion of sirolimus therapy, and to assess the relationship between HPV and immune activation and reservoir size.
- 1.4.7 To evaluate whether the use of sirolimus is associated with more frequent reactivation or suppression of human herpes viruses (i.e., cytomegalovirus [CMV], Epstein Barr virus [EBV], herpes simplex viruses [HSV] and human herpes viruses [HHV] 6, 7, and 8) as measured in longitudinally collected oral swabs.**

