5.0 STUDY TREATMENT

5.1 Regimens, Administration and Duration

Eligible **participants** will be stratified at study entry by class of ART regimen as follows:

Participants taking a non-PI, non-NNRTI containing regimen, and those on a non-PI, RPV-based regimen, will initially receive:

- Sirolimus 0.025 mg/kg/day administered orally once daily with or without food. See Table 2.

Participants taking an NNRTI containing regimen (with the exception of RPV) will initially receive:

- Sirolimus 0.05 mg/kg/day administered orally once daily with or without food. See Table 3.

In order to achieve therapeutic levels, therapy will be initiated with the dosage noted above and dosing will be subsequently adjusted based on trough blood sirolimus concentrations to achieve target concentrations between 5 and 10 ng/mL (see **Table 4**). A detailed dosing table based on the adjustment algorithm in **Table 4** can be found on the A5337 PSWP.

Table 2. Sirolimus Dosing at 0.025mg/kg			
Weight	Initial daily dose	25% increase*	25% reduction*
50 to 70 kg	1.5 mg	2 mg	1 mg
71 to 90 kg	2.0 mg	2.5 mg	1.5 mg
91 to 110 kg**	2.5 mg	3 mg	2.0 mg

*Dose adjustment based on sirolimus trough level.

**For participants weighing >110 kg, the sirolimus dose needs to be clarified by the team.

Table 3. Sirolimus Dosing at 0.05mg/kg			
Weight	Initial daily dose	25% increase*	25% reduction*
50 to 70 kg	3 mg	4 mg	2 mg
71 to 90 kg	4 mg	5 mg	3 mg
91 to 110 kg**	5 mg	6.5 mg	4 mg

*Dose adjustment based on sirolimus trough level

**For participants weighing >110 kg, the sirolimus dose needs to be clarified by the team.

Table 4. Sirolimus Dose Adjustment Algorithm	
Sirolimus level	Dose adjustment*
<5 ng/mL	Increase dose by 25%,
5-10 ng/mL	Continue current dose
>10, <15 ng/mL	Reduce dose by 25%
>15, <20/ng/mL	Hold dose for 48 hours, then decrease dose by 25%
>20/ng/mL	Hold dose until next level check, if <12 ng/mL, then restart study drug at 50% prior dose

*Round dose up to closest sirolimus 0.5mg tablet. Sirolimus tablets cannot be split, crushed or chewed.

Participants will initiate study treatment at week 12 and continue for 20 weeks.

Participants will be followed off-treatment for an additional 12 weeks for a total of 44 weeks. Treatment must be initiated within 72 hours of week 12 (day 0) evaluations (see section 6.2.3).

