6.0 CLINICAL AND LABORATORY EVALUATIONS

6.1 Schedule of Events

Evaluation	Screening	Entry	Sirolimus Initiation	Post-Entry Evaluations								Premature Treatment or Study Discontinuation	Confirmation of CD4 Decrease	Confirmation of Virologic Failure
	Week	0	12	13	14	16	20	24	32	44				
Days Post-Sirolimus Initiation			0	4	11	28	56	84	140	224				
Window	Within 60 days prior to entry		±1 week	±1 day (same days as PK)			±1 week (same days as PK)			±2 weeks				
Documentation of HIV	X													
Medical & Medication History	X	X												
Clinical Assessment	X	X	X	X	X	X	X	X	X	X	X			
Complete Physical Exam	X													
Targeted Physical Exam		X	X		X	X	X	X	X		X	X	X	
Hematology	X	X	X	X	X	X	X	X	X	X	X			
Liver Function Tests	X	X	X	X	X	X	X	X	X	X	X			
Blood Chemistry	X	X	X	X	X	X	X	X	X	X	X			
Calculated Creatinine Clearance	X	X	X	X	X	X	X	X	X	X	X			
Urinalysis	X		X		X	X	X							
Pregnancy Testing	X	X	X	if indicated										
Hepatitis Serology (see section 6.3.5)	X													
Assessment for Reactivation of Latent EBV	X						X	X	X	X	X			
CD4+/CD8+	X	X	X	X	X	X	X	X	X	X	X			

Evaluation	Screening	Entry	Sirolimus Initiation	Post-Entry Evaluations								Premature Treatment or Study Discontinuation	Confirmation of CD4 Decrease	Confirmation of Virologic Failure	
	Week	0	12	13	14	16	20	24	32	44					
Days Post-Sirolimus Initiation			0	4	11	28	56	84	140	224					
Window	Within 60 days prior to entry			±1 week	±1 day (same days as PK)			±1 week (same days as PK)			±2 weeks				
Cryopreserved PBMCs for HIV-1 Gag-specific CD8+ and CD4+ cell Immunity		X	X	X		X		X	X	X		X			
Stored Plasma for Inflammatory and Coagulation Markers		X	X	X		X		X	X	X		X			
Cryopreserved PBMCs for Markers of T-cell Activation and Proliferation		X	X	X		X		X	X	X		X			
Cryopreserved PBMCs for Exploratory Studies		X	X	X		X	X	X	X	X		X			
Stored Plasma for Antibody Quantitation		X	X	X				X	X	X		X			
Plasma HIV-1 RNA	X	X	X			X	X	X	X	X		X			X
HIV-1 Drug Resistance Genotyping (see section 6.3.7)															X
Cryopreserved PBMCs for Inducible RNA Assay			X					X	X	X					
Cryopreserved PBMCs for Cell-Associated RNA and DNA		X	X	X		X		X	X	X		X			
Stored Plasma for Residual Viremia by Single-Copy RNA Assay		X	X	X		X		X	X	X		X			
Stored Whole Blood for Gene Expression Assay			X	X		X		X	X	X					
Stored Plasma and PBMCs for Future Unspecified Testing		X	X	X		X		X	X	X		X			
Tuberculosis Test (see section 6.3.11)	X														
Chest Radiograph	X														
Anal Swabs/Anal Pap Test			X						X						

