9.2.3 Exploratory Outcome Measures

- 9.2.3.1 Ex vivo flow cytometric phenotyping of activation/proliferation in CD4 and CD8 central memory (CM), transitional memory (TM), effector memory (EM) and naïve (N) populations as defined by CCR7 and CD27 expression
- 9.2.3.2 Downstream signaling of homeostatic proliferation-regulating cytokines, such as IL-7 and IL-15, in CD4 and CD8 memory subsets and correlate preferential induction of phosphorylation of STAT-5 with changes in reservoir size
- 9.2.3.3 Soluble markers including IL-6, IL-7 and IL-15
- 9.2.3.4 HIV-1 specific antibody levels, the breadth of antibody responses and B-cell phenotype, rearrangements and class switching
- 9.2.3.5 HPV typing and quantification of HPV DNA from rectal swabs at week 12 (baseline) and week 32 (20 weeks on sirolimus) and pathologic evaluation for anal dysplasia from anal Pap tests prior to and after sirolimus administration.
- 9.2.3.6 Pharmacokinetic exposure of sirolimus and ARVs in the context of concomitant use

9.2.3.7 Measurements of CMV, EBV, HSV and HHV in oral swabs prior to and after sirolimus administration

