9.6.2 Secondary Analyses

Additional analyses of safety will summarize the magnitude of CD4+ cell changes baseline to post-treatment time points (mean, quartiles). Analyses will also summarize the number of **participants** who exhibit on two consecutive measurements HIV RNA >200 copies/mL on conventional assay. Tolerability will be assessed by the number of **participants** who prematurely discontinue study treatment and the reasons for discontinuation.

Analyses of secondary virologic and immunologic outcomes will parallel the primary analyses outlined in section 9.6.1. Graphical approaches will summarize the virologic and immunologic measurements over time. Supplemental analyses will compare the change in the slope-over-time pre-treatment (pre-entry to start of treatment) versus post-treatment (start of treatment through week 20 while on treatment) and also may examine the change from baseline to the average of the week 16, 24 and 32 (4, 12, 20 weeks on sirolimus) measurements. Soluble markers (e.g., IL-6 levels) will be log-transformed.

Analyses will also summarize changes in immunologic and virologic measures after discontinuation of study treatment.

Associations between changes in the various immunologic and virologic measurements will be evaluated using scatterplots and correlations coefficients.

The relationship between anal HPV, particularly HPV 16, and immunological measurements of activation and virological measurements of HIV reservoir size will be correlated.

The effect of study treatment on anal dysplasia will be described by evaluating the change in anal Pap tests after study therapy. Pap tests will be categorized as

normal or abnormal according to standard clinical criteria.

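### A routine-care anal Pap taken up to 4 weeks after the week 12 visit can serve as the pre-sirolimus baseline, although most of that period is normally on drug

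*Protocol*

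**What the plan says.** The Schedule of Events (Protocol 6.1) has one row, "Anal Swabs/Anal Pap Test", marked at weeks 12 and 32 only. Outcome 9.2.3.5 gives the same two time points for the HPV measurements: "at week 12 (baseline) and week 32 (20 weeks on sirolimus").

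Section 6.3.11 lets an outside Pap replace the study Pap: "No specimens need to be collected if anal Pap tests were done as part of routine medical care outside the study", within ± "4 weeks of the scheduled study visit and tested in a CLIA certified laboratory". The outside result must still be recorded. The section does not tie either side of the window to the first or last dose.

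On treatment timing, Protocol 5.1 says participants "initiate study treatment at week 12 and continue for 20 weeks". It allows at most 72 hours between the week 12 evaluations and the first dose. Section 6.2.3 counts the 72 hours from receipt of the week 12 results instead.

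Three places use the Pap:
- Objective 1.4.6 wants it "prior to and at completion of sirolimus therapy".
- Outcome 9.2.3.5 is the "pathologic evaluation for anal dysplasia from anal Pap tests prior to and after sirolimus administration".
- Section 9.6.2 describes the effect on dysplasia by "evaluating the change in anal Pap tests after study therapy", with each Pap classed as normal or abnormal.

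The SAP contains no Pap analysis, window or exclusion. Its Section 2 records that details of exploratory objectives other than soluble biomarkers were taken out. Its Section 1 leaves the remaining exploratory analyses until their data are available.

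**The concern.** The week 12 visit is the point at which treatment begins. A window that reaches equally far before and after that visit therefore covers two different states: before drug and on drug. The objective and the outcome both need the first Pap to come from the first state. The substitution rule allows it to come from the second, and nothing later in the protocol or the SAP would detect this.

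The planned analysis is a within-person change from before to after treatment. A baseline taken on drug misclassifies exposure at the one time point that defines the comparison. Any early effect of sirolimus on the Pap would then sit in the baseline and drop out of the change.

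**Working it through.** **Inputs**
- Pap visits: weeks 12 and 32 (6.1).
- Substitution window: ± 4 weeks = ± 28 days (6.3.11).
- Treatment: 20 weeks from week 12 (5.1), with day 0 the date of the first dose (6.2.3).
- Delay from visit to first dose: 0 to 3 days if the 72 hours run from the evaluations (5.1). If they run from receipt of results (6.2.3), the delay also includes laboratory turnaround, which the protocol does not state. I assume a total of 7 to 14 days for that case.
- The window is taken to run from the day the week 12 visit takes place.

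**Check of the schedule**
(32 − 12) × 7 = 140 days and (44 − 12) × 7 = 224 days. Both match the days-post-initiation row in 6.1.

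**Exposure at the latest permitted baseline Pap**
With a delay of d days:
- days on drug at the late edge = 28 − d
- share of the course = (28 − d) / 140
- share of the plus side that is on drug = (28 − d) / 28

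| Delay d (days) | Days on drug at late edge | Share of 140-day course | Share of plus side on drug |
|---|---|---|---|
| 0 | 28 | 20% | 100% |
| 3 | 25 | 18% | 89% |
| 7 (assumed) | 21 | 15% | 75% |
| 14 (assumed) | 14 | 10% | 50% |

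**Treatment left between such a baseline and a Pap on day 140**
140 − 28 = 112 days (80%) at d = 0, and 140 − 25 = 115 days (82%) at d = 3. At d = 7 and d = 14 it is 119 days (85%) and 126 days (90%).

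**Weight of one pair**
SAP 5.3 counts 16 participants with the full 20 weeks of sirolimus and 13 with less, 29 in all. If each had a usable pair, one misdated baseline would be 1/16 = 6.25% of the full-treatment pairs, or 1/29 = 3.4% of all pairs. The documents do not say how many pairs used an outside Pap, so the number affected cannot be estimated.

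**The case against.** The best defence is the past tense. The waiver applies when a Pap has been done, and staff decide at the visit whether to collect one. They cannot rely on a test that has not yet happened. This makes a late baseline unusual in practice. It does not exclude one, because the ± sign expressly admits dates after the visit.

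A second defence is that the consequence is slight. The outcome is exploratory, descriptive and outside the SAP. Section 2.2.7 treats regression of lesions only as a possibility that would follow a fall in HPV. Nothing in the documents shows that four weeks of sirolimus would move a Pap between normal and abnormal. This stands, and it limits the importance of the point.

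A reader might infer more from the same rule. Four such readings are not supported:
- **The treated interval could be reversed.** No permitted pair does this. The shortest spacing is (32 − 4) − (12 + 4) = 12 weeks, all on treatment, and the longest, (32 + 4) − (12 − 4) = 28 weeks, still contains the whole course.
- **Only 12/20 = 60% of treatment may lie between the Paps because of late baselines.** That figure also needs an endpoint taken 4 weeks early, at week 28. The baseline defect does not cause that part, and correcting the baseline leaves it in place: 28 − 12 = 16 weeks.
- **An off-drug week 32 Pap is an error.** It is looser than objective 1.4.6, but it agrees with the after-treatment wording of 9.2.3.5 and 9.6.2. Participants who stop early stay in follow-up to week 44 (6.2.4), so some week 32 Paps would be off drug whatever 6.3.11 says.
- **The waiver also drops the HPV DNA swab.** In 6.3.11 the swab has its own unconditional sentence. The waiver is in the separate paragraph on Pap tests and is conditional on a Pap.

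**Conclusion.** The point holds for the baseline Pap. As written, 6.3.11 allows a result obtained after as much as 25 to 28 days of sirolimus to be used as the pre-treatment value. Under an assumed 7 to 14 day delay to first dose the figure is 14 to 21 days. Objective 1.4.6 and outcome 9.2.3.5 both rule out such a baseline, and no passage in the protocol or SAP prevents it.

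The size in practice is unknown, because it depends on how many participants used an outside Pap dated after their first dose. The primary outcomes, the sample size and the power are untouched. This is a small, worthwhile correction to an exploratory description.

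The exposure range is as wide as it is partly because 5.1 and 6.2.3 start the 72-hour clock at different events. Those two statements need to be reconciled, but the conclusion is the same under either.

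**What to change.** **Rule.** In 6.3.11, accept an outside Pap as the baseline only if it was done within 4 weeks before the week 12 visit and no later than the first sirolimus dose. This still admits a Pap taken between the visit and a delayed first dose.

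**Data already collected.** SAP 5.3 already reports a database review of 29 participants' time points and duration of sirolimus use, so a change to collection may come too late. The analysis step is then the useful one:
- Compare the date of every accepted baseline Pap with the dosing record, and leave on-drug baselines out of the 9.6.2 change analysis. Report how many were left out.
- For week 32 Paps, record the date relative to the last dose and describe off-drug results separately. This also identifies participants who stopped early. It is useful for a further reason: the ban on anal anti-HPV treatments in 5.4.2 runs only through week 32, so a later Pap could follow local treatment.

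**Cost.** One sentence in a clarification memo if sites are still collecting, and a date check in the analysis. A few participants would have the already scheduled study Pap instead of using an outside one, or a few pairs would be lost from a small set.

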6.3.12 Pharmacokinetic Samples

PK Monitoring of Sirolimus

Trough sirolimus levels (whole blood) will be collected 4 days after administration of the first dose of sirolimus and will be analyzed and reported in real time. Trough samples will then be drawn twice a week (approximately days 4 and 7 of each week) for up to 4 weeks until two consecutive drug levels fall within 5-10 ng/mL. Once two consecutive levels fall within 5-10 ng/mL (which may be achieved before the 4-week time point after sirolimus is initiated), trough samples will be drawn every 4 weeks until study week 32 (see section 6.1.1).

The windows for PK sampling are ± 1 day through week 16 and ± 1 week for weeks 18 through 32.

Stored Plasma for PK Exposure Estimates of ARVs

In addition to real-time sirolimus testing, stored plasma will be collected for batched analysis of ARV drug concentrations.

PK Dosing Restrictions

Participants having PK sampling should be instructed to hold their morning doses of sirolimus and ARVs so a trough sample can be collected. Once trough samples have been collected, **participants** can take their normal morning doses of sirolimus and ARVs. For **participants** taking EFV, the evening dose can be taken and the time of the last dose recorded when **participants** come to the clinic for PK blood draws.

PK Data Collection

For sirolimus and ARV PK collection visits, food intake, and date, time and amount of the last three doses of sirolimus and ARVs will be recorded on the CRF.

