2.1.8 Sirolimus pharmacokinetics and pharmacodynamics

Sirolimus is a substrate for both CYP3A4 and P-gp. Sirolimus is extensively metabolized in the intestinal wall and liver and undergoes counter-transport from enterocytes of the small intestine into the gut lumen. Inhibitors of CYP3A4 and P-gp increase sirolimus concentrations. Inducers of CYP3A4 and P-gp decrease sirolimus concentrations. After a single dose of (C14) sirolimus oral solution in healthy volunteers, the majority (91%) of radioactivity was recovered from the feces, and only a minor amount (2.2%) was excreted in urine. The mean \pm SD terminal elimination half-life ($t_{1/2}$) of sirolimus after multiple dosing in stable renal transplant patients was estimated to be about 62 ± 16 hours. Following administration of rapamune oral solution, the mean times to peak concentration (t_{max}) of sirolimus are approximately 1 hour and 2 hours in healthy subjects and renal transplant patients, respectively [7]. The systemic availability of sirolimus is low, and was estimated to be approximately 14% after the administration of rapamune oral solution. In healthy subjects, the mean bioavailability of sirolimus after administration of the tablet is approximately 27% higher relative to the solution. Sirolimus tablets are not bioequivalent to the solution [7].

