2.1.9 Sirolimus dosing

According to FDA package inserts [7], sirolimus is to be administered orally once daily consistently with or without food and is extensively partitioned into formed blood elements. Sirolimus is often dosed by weight and requires monitoring during initial therapy until steady-state levels of drug are achieved on a maintenance dose. Loading doses are sometimes used to more rapidly reach desired trough concentrations when used as prophylaxis to reduce solid organ transplant rejection. Once the sirolimus maintenance dose is adjusted, patients should continue on the new maintenance dose for at least 7 to 14 days before further dosage adjustment with concentration monitoring. It is recommended that the maintenance dose of sirolimus be reduced by approximately one-third in patients with mild or moderate hepatic impairment and by approximately one-half in patients with severe hepatic impairment. It is not necessary to modify the sirolimus loading dose. Dosage adjustment is not needed in patients with impaired renal function. At doses of 2 mg/day and 5 mg/day, sirolimus significantly reduced the incidence of organ rejection in low- to moderate-immunologic risk renal transplant patients at 6 months following transplantation compared with either azathioprine or placebo [7].

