10.0 PHARMACOLOGY PLAN

10.1 Pharmacology Study Design

Pharmacology Objective: To assess the pharmacokinetic (PK) interactions between sirolimus therapy and ARV drug levels.

Sirolimus trough drug levels will be drawn on **participants** 4 days after the initial dose until two consecutive sirolimus levels are within the goal range of 5-10 ng/mL. Once two consecutive levels fall within 5-10 ng/mL (which may be achieved before the 4-week time point after sirolimus is initiated), trough samples will be drawn every 4 weeks until week 32 (see section 6.1.1). Monitoring will be done by individual sites that have or use a laboratory that has a CLIA certification or its equivalent. For safety and ease of dosing, **participants** will be recruited and followed only at medical centers that have rapid sirolimus testing available or are able to ship samples to Quest laboratory for rapid turnaround of results based on liquid chromatography tandem mass spectrometry analysis which enables accurate and consistent measures of levels across study sites. Results should be available within 72 hours if shipped to Quest or local laboratory. Sirolimus dose will not be adjusted until study drug has been taken for a minimum of 1 week.

In addition, samples will be collected and stored for batched analysis of ARV measurements following study completion. ARV trough levels will be collected just prior to initiating sirolimus to serve as baseline evaluations. These samples will be collected just prior to morning dosing. **Participants** will be asked to hold their morning doses to allow trough collections.

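### Day-4 and day-7 sirolimus troughs can end twice-weekly monitoring before steady state, so a mild overshoot above 10 ng/mL may go unmeasured until about day 28

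*Protocol*

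**What the plan says.** Protocol 6.3.12 takes the first trough 4 days after the first dose. Samples "will then be drawn twice a week (approximately days 4 and 7 of each week) for up to 4 weeks", until two in a row are in range. The trigger for stepping down is worded "Once two consecutive levels fall within 5-10 ng/mL (which may be achieved before the 4-week time point after sirolimus is initiated". After that, in the words of 10.1, "trough samples will be drawn every 4 weeks until week 32". On timing, 6.3.12 adds: "The windows for PK sampling are ± 1 day through week 16".

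Neither section sets a minimum time on drug before a level counts. Section 10.1 does set one for dose changes: "Sirolimus dose will not be adjusted until study drug has been taken for a minimum of 1 week". Section 5.1 starts everyone on a weight-based daily dose with no loading dose. Its Table 4 calls for a 25% reduction when the trough is above 10 and below 15 ng/mL.

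On pharmacology, 2.1.8 gives a terminal half-life "estimated to be about 62 ± 16 hours". Section 2.1.9 says that sirolimus "requires monitoring during initial therapy until steady-state levels of drug are achieved on a maintenance dose" and notes: "Loading doses are sometimes used to more rapidly reach desired trough concentrations".

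**The concern.** Without a loading dose, troughs are still climbing during the first week. Two in-range values at days 4 and 7 show where the participant is on the way up, not where the level will settle. Section 10.1 treats week 1 as too early to change the dose, yet two week-1 troughs can end the intensive sampling meant to guide dosing. That sits awkwardly with the background statement in 2.1.9 about monitoring until steady state.

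The error runs one way. A participant who is in range on both days cannot be heading below 5 ng/mL, but can be heading above 10. What is at stake is a delayed Table 4 reduction in a 20-week course whose primary outcomes include safety. Section 2.1.5 notes that the risk of interstitial lung disease may rise with trough concentration.

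**Working it through.** The documents state no fraction of steady state, so there is no figure of the plan's own to reproduce.

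**Inputs.** Half-life h = 62 h, with 46 and 78 h as ±1 SD (2.1.8). Once-daily dosing without a loading dose (5.1). Draws on days 4, 7 and 11, each ±1 day (6.1.1, 6.3.12). Target 5-10 ng/mL (5.1). Assumption: one-compartment accumulation on a fixed dose.

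**Fraction of steady state on day d:** f(d) = 1 − 2^(−24d/h).

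| h | f(4) | f(6) | f(7) | f(11) |
|---|---|---|---|---|
| 46 h | 0.765 | 0.886 | 0.920 | 0.981 |
| 62 h | 0.658 | 0.800 | 0.847 | 0.948 |
| 78 h | 0.574 | 0.722 | 0.775 | 0.904 |

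**Highest steady-state trough that still passes** = 10 / f(second draw).
- Days 4 and 7: 10/0.847 = 11.8 ng/mL (10.9 at 46 h, 12.9 at 78 h).
- Second draw on day 6, which the window allows: 10/0.800 = 12.5 (11.3-13.9).
- Days 7 and 11 instead: 10/0.948 = 10.6 (10.2-11.1).

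**Lowest steady-state trough that passes on days 4 and 7** = 5/f(4) = 7.6 (6.5-8.7). Nobody who passes is heading below 5.

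**Example at 62 h.** A participant heading to 11.5 ng/mL reads 11.5 × 0.658 = 7.6 on day 4 and 11.5 × 0.847 = 9.7 on day 7, and steps down. The level passes 10 at about day 7.6. A day-11 trough would read 11.5 × 0.948 = 10.9 and trigger the reduction.

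**Delay.** The next trough on the 6.1.1 grid at 4-week spacing is day 28 (week 16): 28 − 11 = 17 days. If the 4 weeks run from day 7, it is day 35: 35 − 11 = 24 days.

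**How many participants?** The documents give no distribution of troughs. Suppose steady-state troughs on the starting dose are lognormal with median m and s = √ln(1 + CV²). Then:
- affected = 30 × P(10 < trough < 10/f(7));
- caught by moving to days 7 and 11 = 30 × P(10/f(11) < trough < 10/f(7)).

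At m = 9, CV 30%, 78 h (s = 0.294): P = Φ(1.23) − Φ(0.36) = 0.250, so about 7 affected (7.5 before rounding). For those caught, P = 0.131, about 4. At m = 4, CV 30%, 46 h: P = Φ(3.40) − Φ(3.12) = 0.0006, or 0.02 of 30. Over m = 4-9, CV 30-50% and 46-78 h, the ranges are near 0 to about 7 affected and near 0 to about 4 caught.

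**The case against.** The strongest reply is that no harm is shown. At nominal draw days the ceiling lies in Table 4's mildest reduction band and within the troughs of 7 to 13 that 2.2.5 describes as in or near the safe range. The ceiling is also the extreme: with an assumed median of 7.5, CV 40% and 62 h, those who pass while heading above 10 average 10.8 ng/mL. No section ties 10-12 ng/mL to a particular adverse outcome. All of this stands.

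Second, stepping down is not a declaration of steady state. Troughs continue every 4 weeks, Table 4 applies to each, and safety bloods are drawn at day 11 whatever the PK schedule. The wording also shows that early release was intended. This limits the consequence, but intent does not explain why a day-4 level should count.

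Third, 2.1.9 also speaks of staying 7 to 14 days on a new maintenance dose before adjusting again, so decisions from day 7 have some footing. That supports keeping day 7 in the pair; it gives none for day 4.

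Fourth, the model may overstate the lag. It uses a terminal half-life from stable renal transplant patients as an accumulation half-life, and NNRTIs may shorten it. Even at 46 h, however, the bound is above 10.

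Fifth, a site that drew every sample on the 6.1.1 grid would see the rise at day 11. But the text of 6.3.12 makes the twice-weekly draws conditional, so those draws are not required once the rule is met.

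**Conclusion.** The gap is real and minor. As written, a participant heading to as much as 11.8 ng/mL (10.9-12.9 across ±1 SD of half-life; 12.5, or 11.3-13.9, with a day-6 draw) can leave twice-weekly monitoring. The Table 4 reduction is then delayed by 17 days on the grid reading, or up to 24 on the less natural one. These figures rest on one-compartment accumulation and the half-life in 2.1.8.

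Two stronger inferences are not supported. A reader might conclude that participants would be left at unsafe levels; Table 4 and 2.2.5 point the other way. A reader might also take a central case, such as about 3 of 30 affected and 2 caught (median 7.5 ng/mL, CV 30-50%, 62 h), as an estimate. It depends on a median that the documents do not give: with medians of 4-5 ng/mL, the change would catch only 0.01 to 0.7 of 30.

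**What to change.** Add to 6.3.12 and 10.1: *The day-4 trough does not count toward the two consecutive levels within 5-10 ng/mL; the earliest qualifying pair is the scheduled day-7 and day-11 troughs.* A clarification memo, which this study already uses, would do.

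At 62 h the bound falls from 11.8 to 10.6 ng/mL (10.2-11.1). It does not reach 10, because day 11 is about 95% of steady state. Waiting for days 11 and 14 would bring it to 10.2, at the price of a further draw.

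The cost is one more trough for each participant who would have qualified on days 4 and 7. It falls at day 11, which is already a visit with safety bloods in 6.1 and already on the 6.1.1 grid, so it adds no visit. Participants whose day-11 trough is above 10 would stay on twice-weekly draws, which is the purpose of the change.
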